Statistical Analysis Plan

A Prospective Study of Human Bone Adaptation Using a Novel in Vivo Loading Model

ID: 13-111

NCT #: not yet assigned

Originally created: 1/12/2012

Last updated: 1/12/2012 by [name]

Statistical Analysis Plan

Originally created: 1/12/2012

Last updated: 1/12/2012 by [name]

Statistics and Expected Outcomes:

An intent to treat analysis will not be employed here because the purpose of this research is to determine the link between *actual strains applied to bone* and the bone adaptive response. The present study is not intended to address the degree to which mechanical loading is an effective means to improve bone strength in a public health setting. Accordingly, adherence to the mechanical loading protocol is expected to influence the degree of adaptation and will be considered a potential explanatory variable for the following analyses.

For Experiment 1, hypotheses are related to the effect of strain magnitude.

For Experiment 2, hypotheses are related to the effect of strain rate. In both cases, the statistical analysis plan is the same, but tests will be performed on the corresponding variables (strain magnitude, or strain rate).

Hypothesis 1a: Bone mass will increase proportionally to the applied strain.

This hypothesis will be tested in two ways. In the first analysis, subjects will be analyzed by group (control, low, and high strain magnitude groups). For the group analysis, the 12-month change in whole radius total BMC will be analyzed as the primary dependent variable in a linear regression model with coefficients representing contrasts between each of the two experimental groups and the control group. Secondary outcome measures of trabecular BMC, ultra-distal BMC, fracture strength, moments of inertia, and others, will also be compared between groups using regression models for change scores at each of the four time points.

If our hypothesis is supported then there will be little change in the control group, a small but significantly higher increase in the 1800 $\mu\epsilon$ group, and a large and significantly higher increase in the 3600 $\mu\epsilon$ group. Similar models will be fit predicting change from baseline to 3, 6, and 9 months.

In the second analysis, we will consider the *actual* strain magnitudes achieved by each subject, (which may differ from the group assigned strain), as a continuous variable, and will set the strain magnitude for control subjects to zero. The underlying assumption in doing this is that the baseline daily activity for *all* subjects is approximately equal, and is sufficient to maintain bone homeostasis. For this analysis, all four time points will be combined into a single model to examine changes across time after the loading regime has ended, and to compare the levels of applied strain. The dependent variable is the change score (in whole radius total BMC) from baseline; the independent variables are level of strain, time (3, 6, 9, 12 months), and a random intercept term for each subject to handle collinearity within repeated measurements. As in the first analysis method, secondary outcome measures of regional BMC, fracture strength, and others, will be considered as well.

If our hypothesis is supported then strain magnitude will be a significant predictor of change in whole radius total BMC and other related variables.

Hypothesis 1b: High initial bone mass, physical activity levels, and grip strength will be associated with diminished adaptive response for a given strain magnitude.

To test this hypothesis, initial BMC, grip strength, and physical activity will be added as potential covariates for the statistical models described in Hypothesis 1a.

If our hypothesis is supported then we would expect to observe an inverse relationship (negative coefficient) between initial bone mass, physical activity, grip strength, and change in BMC per group or per unit applied strain.

Hypothesis 1c: Bone structural changes will include increases in cortical diameter and thickness, and increased trabecular bone mass near the endosteal surface.

To test this hypothesis, the following variables will be examined:

For cortical diameter and thickness: integral and cortical bone mass and bone volume, compressive and bending strength index, and cross-sectional moments of inertia (bending and torsional)

For trabecular bone: trabecular bone mass and volume, cross sectional trabecular moments of inertia

Using the methods described for testing hypothesis 1a, changes in each of the specific variables listed will be examined at each time point. Here, the primary interest is in which specific quantities show the largest strain-related change.

If our hypothesis is supported, we would expect to observe significant strain-dependant increases in each of the variables listed for the experimental groups, but not in the control group.

Hypothesis 1d: Local regions experiencing high strain magnitudes will experience greater local increases in BMC than regions experiencing low strain magnitudes.

This hypothesis will be tested using only subjects in the experimental conditions. For each subject, all of the elements within the baseline FE model will be divided into quartiles based on actual Von Mises equivalent strain occurring within each element. Of interest for the present analysis are elements in the highest strain quartile and the lowest strain quartile. (Note that Von Mises equivalent strains always have a positive sign.) For each of these quartile groups the change in QCT voxel density for those voxels corresponding to the location of the elements will be determined. We will use a Student's t-test to compare the average voxel density change in high strain versus low strain quartiles.

If our hypothesis is supported then elements experiencing the highest Von Mises strain will have significantly greater increases in density compared to elements experiencing the lowest Von Mises strain. Our underlying assumption in using the highest and lowest quartiles is that a minimum strain threshold is required to initiate an increase in density. Therefore, including all elements in the analysis, most of which do not exceed this threshold, may make it difficult to detect a local effect, if one is present.

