Volunteers will be recruited from the communities surrounding Worcester Polytechnic Institute (WPI) including announcements made electronically and in person by members of the research team. Flyers and pamphlets explaining the study will be placed in the community, and, with permission, in the waiting room of the Family Practice clinic at the University of Massachusetts Medical Center. We will work with the institutional review board at WPI to ensure that all subject recruitment materials are compliant.

Screening:

All subjects will be verbally screened for inclusion/exclusion criteria by a member of the research team prior to being invited for a screening visit. During the screening visit, the subject's height and weight will be recorded. Subjects will receive a DXA scan of their nondominant radius and only those with BMD that falls within the specified range for inclusion will participate. Subjects will then visit the Quest Diagnostics Collection Center. There, six ml blood will be drawn via standard veinpuncture and sent to a local diagnostic laboratory (Quest Diagnostics) for a full metabolic profile including measurement of TSH, estradiol levels and Vitamin D concentration (total and 25,OH D₂ and D₃). This data will be interpreted by Drs. [name] and [name]. Potential subjects who have abnormal data and do not qualify for participation will be contacted by [name], given a copy of their laboratory results, and advised to consult their primary care physician. [name] will provide each of these individuals with his own clinical interpretation of the data, so that they understand the importance of their results.

All potential subjects who qualify to participate based on their screening will be invited to participate in the study. A signature of the informed consent document is considered a subject's written affirmation that she fits the inclusion/exclusion criteria.

Group Assignment:

For each Aim, eligible subjects will be randomized to one of two loading groups: a low, or a high group (20 subjects each) by having subjects draw a sealed envelope containing the group assignment. An additional 20 subjects will be randomized to a control (observation only) group. It is not possible to blind subjects or all team members to group assignment due to the nature of the experiment (team members cannot be blinded because group assignments must be known to assign target forces). However, all data will be blinded for analysis.

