- For Aim 1 the low and high groups refer to low and high strain magnitude. Subjects in each of these groups will be assigned a target force based on their individual anatomy and their group assignment. The low and high strain groups will be assigned strain magnitudes of 1800 micro-strain ($\mu\epsilon$) and 3600 $\mu\epsilon$ respectively. The forces required to produce these strains typically range from 300 to 500 N (0.5 to 0.8 body-weights).
- For Aim 2 the low and high groups refer to low and high strain rate. Subjects in each of these groups will be assigned a target force based on their individual anatomy, and will be given one of two instruction sets that will assist subjects in producing slower or more rapid forces. The slow strain rate group will be given a target loading rate of 4500 $\mu\epsilon/s$ (i.e., 3600 $\mu\epsilon$ achieved in 0.8 seconds. The impact strain rate group will be given a target loading rate of 36,000 $\mu\epsilon/s$ (i.e., 3600 $\mu\epsilon$ achieved in 0.1 seconds). The slow group will be instructed, "Each time you hear a beep, lean on your hand to reach the target force, loading and unloading your hand as slowly and evenly as possible." In pilot subjects, this resulted in a load application time of 0.8 seconds. The impact group will be instructed to "Stand approximately 15 inches away from the device (which is placed on a hip-high table). When you hear a beep, fall forward until your hand contacts the load cell. You may need to adjust how close you stand to achieve your target force." In pilot subjects this resulted in a load application time of 0.1 seconds. Subjects in the control group will continue their regular physical activity.

Rationale for Doses:

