- For Aim 1, to determine the target strain range, pilot subjects were classified as high and low responders (five and three subjects, respectively, based on observed 14 week changes in ultradistal BMC of $+2.57\%$ and $+0.51\%$). On average the high responders' peak Von Mises equivalent strains within the ultradistal volume were $3430\pm536\text{ }\mu\epsilon$, whereas the low responders' were $2125\pm432\text{ }\mu\epsilon$. Based on these results, we conclude strains below $1800\text{ }\mu\epsilon$ are unlikely to elicit a response, whereas we observed that strains above $3600\text{ }\mu\epsilon$ required forces in excess of 450 N for the average subject. Many women have difficulty applying this magnitude. Thus, targets of 1800 and $3600\text{ }\mu\epsilon$ were identified for this experiment.
- For Aim 2, the target strain magnitude, $3600\text{ }\mu\epsilon$, represents the largest strain magnitude that is achievable voluntarily by most female subjects. In our pilot subjects, this required a target force of $445\pm80\text{ N}$. Using the largest reasonable strain value maximizes the possible strain rate that is achieved with the impact loading group and maximizes the possibility that the loading elicits an osteogenic response. The strain rates that are assigned, $4500\text{ }\mu\epsilon$ and $36,000\text{ }\mu\epsilon$, respectively, are a function of the load application time generated with each of the two instruction sets. *The range of strain magnitudes produced using “slow” versus “impact” instruction sets represent nearly the entire range that can be voluntarily produced safely and consistently by subjects.*
- In both aims, subjects will apply 100 cycles of loading per day, 4 days per week, for 12 months. In our pilot subjects, this number of cycles per week was well tolerated by subjects and was osteogenic.

b. Sources of Materials

All research data will be obtained from the subjects specifically for research purposes.

- QCT data is uploaded to a secure cloud-based website (www.Lifelimage.com) for transfer to the laboratory. Per hospital procedure, all CT scans are read by a radiologist to ensure that no abnormalities are detected. Should the scan reveal abnormal pathology, the subject will be contacted directly by the radiologist. The CT scan is documented in each subject's medical record as a research CT scan.

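### The SAP's rejection of intention-to-treat reaches the randomised group contrast and lets adherence into it, although the stated reason fits only the achieved-strain analysis

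*SAP*

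**What the plan says.** The opening paragraph of the SAP (Statistics and Expected Outcomes) states: "An intent to treat analysis will not be employed here". The reason given is that the study asks how strain really applied to bone relates to adaptation, not whether loading works as a public-health measure. As a consequence, adherence "will be considered a potential explanatory variable for the following analyses". No analysis is exempted.

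Two analyses of Hypothesis 1a follow:

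- **Group analysis.** 12-month change in whole radius total BMC is regressed on group, with "coefficients representing contrasts between each of the two experimental groups and the control group". Similar models are planned for 3, 6 and 9 months and for secondary outcomes.
- **Achieved-strain analysis.** A repeated-measures model uses the actual "strain magnitudes achieved by each subject, (which may differ from the group assigned strain), as a continuous variable", sets controls to zero, and includes time and a random intercept.

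The SAP applies the same plan to Experiment 2, with strain rate in place of strain magnitude.

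The Protocol (Group Assignment) randomises women to two loading groups per Aim and adds: "An additional 20 subjects will be randomized to a control (observation only) group". Loaded women in Aim 1 are "assigned a target force based on their individual anatomy and their group assignment". The Data and Safety Monitoring Plan allows the prescribed load to be lowered during the study.

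Neither document defines adherence, an adherence threshold, a value for controls, or an analysis set for the group regression.

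**The concern.** The group regression is the analysis that rests on randomisation. Its protection depends on comparing women as assigned and on not conditioning on anything that happens afterwards. Adherence and achieved strain both happen afterwards, and in controls they have no meaning.

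The opening paragraph leaves two things open for this contrast:

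1. Adherence may be added as a covariate. The group coefficients, which the SAP takes as the contrasts, then describe loading at whatever adherence value controls were given. A coefficient read at zero adherence could be reported as the effect of loading.
2. With intention-to-treat set aside and nothing put in its place, a reader cannot tell which women enter the contrast. Any exclusion for low adherence or missed strain could fall only on loaded women.

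**Working it through.** **Step 1. Does the stated reason cover both analyses?** The reason concerns strain actually applied. The achieved-strain model uses that quantity directly, so not analysing by assignment is coherent there. That model contains strain and time but not sessions completed, so adherence may add real exposure information to it. The group regression has no achieved-strain term. It estimates the difference between assigned groups, and the stated reason gives no ground for conditioning that difference on adherence.

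**Step 2. What adding adherence does to the group coefficient.** Take the group model with adherence A added and every control coded k:

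y = a + bL·Low + bH·High + c·A + error

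Least-squares residuals sum to zero within each group, so

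- mean of controls = a + c·k
- mean of high group = a + bH + c·(mean A in high group)

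Subtracting gives bH = D − c·(mean A in high group − k), where D is the plain high-minus-control difference. Controls do not vary in A, so c is estimated from loaded women only and does not depend on k. Changing k therefore alters neither the fit nor the contrast at mean high-group adherence, which is always D. It alters only the printed bH.

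**Step 3. Illustration.** The documents give no adherence data and no SD of BMC change. Assumed: 20 per group, residual SD 1, mean adherence 0.7 (SD 0.2) in both loading groups, and effects of 1 SD (high) and 0.5 SD (low) proportional to adherence.

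- Pooled slope: c = (1/0.7 + 0.5/0.7)/2 = (1.429 + 0.714)/2 = 1.071
- SE of c: √[1/(2 × 19 × 0.2²)] = √(1/1.52) = 0.811
- SE of bH: √[2/20 + (0.7 − k)² × 0.811²]

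| Coding of controls | Printed bH (SD) | Approximate SE |
|---|---|---|
| 0 | 1 − 1.071 × 0.7 = 0.25 | √(0.100 + 0.322) = 0.65 |
| 1 | 1 + 1.071 × 0.3 = 1.32 | √(0.100 + 0.059) = 0.40 |
| Adherence centred within arm | 1.00 | √0.100 = 0.32 |

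A simulation of 8,000 trials under these assumptions gave 0.26, 1.32 and 1.00. Fitted values agreed across codings to 9e-14, and the contrast at mean high-group adherence was 1.00 (SE 0.32) each time.

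**Step 4. Exclusions.** There is no rule to put numbers into. What the text does show is that any cut on adherence or achieved strain could remove women only from the loading groups, because controls have no value on either.

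**The case against.** The strongest reply is that the SAP describes modelling, not exclusion. It presents the adherence variable as what follows from rejecting intention-to-treat. Its second analysis keeps women whose strain differs from assignment. Where it does restrict subjects (Hypothesis 1d, loaded women only), it says so. The most natural meaning of group is assigned group, and the group model as written lists no adherence term. All of this stands: the harm is permitted, not planned.

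A reader might go further and infer that about half the high group would be lost. Under Rationale for Doses the Protocol says "In our pilot subjects, this required a target force of" 445±80 N for 3600 microstrain, and the monitoring plan names 450 N as a limit. Taking ± as a normal SD, 1 − Φ((450 − 445)/80) = 47.5% would fall short; allowing a 10% shortfall (450/0.9 = 500 N) it is 1 − Φ((500 − 445)/80) = 24.6%. The arithmetic is right, but the documents do not support the inference. No passage excludes women for missing 3600 microstrain. The 450 N limit also does not match the 300 to 500 N given under Group Assignment and Protection Against Risk; those passages need reconciling in their own right.

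A reader might also infer an inflated type I error, citing Hypothesis 1b: "High initial bone mass, physical activity levels, and grip strength will be associated with diminished adaptive response for a given strain magnitude". That hypothesis concerns response at a given strain. It says nothing about BMC change without a loading effect, so it does not support such figures. Exclusion unrelated to outcome gives no bias, and any other correlation would be the reviewer's assumption.

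Two further points have weight. The Protocol says data will be blinded for analysis, which reduces the scope for data-driven choices, although only loaded women would have adherence records. And the mechanistic aim is a reasoned choice. Neither justifies adjusting the randomised contrast for adherence, and the aim keeps its place in the second analysis.

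**Conclusion.** The concern holds in limited form. The SAP rejects intention-to-treat for all analyses and admits adherence to the group-versus-control regression, for a reason that fits only the achieved-strain analysis. This is a stated rule, not merely missing detail.

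The adjustment problem is one of reporting. Under the assumptions in the working, the same fit can print anything from 0.25 to 1.32 SD for a contrast of 1.00 SD at mean adherence. These are not three competing results, and large false-positive rates should not be read into them. The exclusion problem is an open door only: its share, bias, power loss and type I error cannot be estimated from the documents.

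It is worth correcting because the correction is cheap and protects the randomised comparison on the primary outcome.

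**What to change.** Confine the rejection of intention-to-treat to the achieved-strain analyses, and add to the SAP:

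> The main group analysis includes every randomised woman with outcome data, in her assigned group, whatever her adherence, achieved strain or any load reduction. It contains no adherence or achieved-strain covariate.

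- Use adherence and achieved strain in the second analysis, labelled as a non-randomised dose-response analysis.
- Treat any group model with adherence as supplementary, with adherence centred within arm.
- Apply the same wording to Experiment 2.

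The cost is SAP text only; both analyses are already planned. There are two downsides. The group contrast will be diluted by non-adherence, and a set limited to women with outcome data leaves bias from dropout, which needs its own missing-data rule.

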Although an older (potentially osteoporotic) subject population is of clinical relevance, the purpose of the present study is to show and define the effect of various aspects of mechanical loading signal. Our pilot data demonstrate that the proposed intervention is osteogenic in the proposed population, which will allow us to further examine these signal characteristics in detail. Ultimately, it is our view that mechanical loading interventions will be *most effective* as a preventive tool to improve peak bone mass and bone mechanical properties in adolescents and younger adults. It has been demonstrated that high levels of physical activity, especially during growth, cause improvements to bone mass and structure that persist throughout the lifespan (Barnekow-Bergqvist, 2006). The notion of maximizing peak bone mass to protect against age-associated declines in bone strength is accepted as logical and reasonable. Given the short-term benefits of the proposed loading regime that we observed in our pilot data, the subjects who participate in this longer-term research study are likely to experience clinically relevant increases in distal radius peak bone mass and mechanical properties, potentially reducing lifetime fracture risk at this site.

Women attain peak BMC and BMD at the ultra-distal radius at age 23 and 19 respectively, and attain 94% and 98% of peak BMC and BMD by age 16 (Henry, 2004). These measures remain at peak until age 40. Changes measured during the proposed study period in a population of 21-40 year old women can, therefore, be attributed to the mechanical loading intervention.

Here we focus on women only. Given the high rate of osteoporosis that this population develops later in life, this seems a well intentioned priority. We intentionally exclude women who were recently pregnant, are lactating, or who have plans to become pregnant. Pregnancy and lactation represent

altered physiologic states that are associated with increased bone turnover. We also exclude children because they have not yet reached skeletal maturity.

Recruitment:

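### The SAP leaves open whether the primary change-score model is adjusted for baseline BMC; make the baseline value a fixed covariate in both Hypothesis 1a models

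*SAP*

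**What the plan says.** In the SAP, Hypothesis 1a, first analysis, "the 12-month change in whole radius total BMC will be analyzed as the primary dependent variable in a linear regression model". The only terms described for it are two comparisons, low and high strain each against control. No baseline term is listed. In the second analysis the outcome is again change from baseline, and "the independent variables are level of strain, time (3, 6, 9, 12 months), and a random intercept term for each subject". Again there is no baseline term. The opening paragraph of the SAP rejects an intention-to-treat analysis and says that adherence "will be considered a potential explanatory variable for the following analyses"; it does not mention baseline BMC there.

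Baseline BMC appears under Hypothesis 1b, where "initial BMC, grip strength, and physical activity will be added as potential covariates" to the Hypothesis 1a models. The hypothesis reads: "High initial bone mass, physical activity levels, and grip strength will be associated with diminished adaptive response for a given strain magnitude". If it is supported, "we would expect to observe an inverse relationship (negative coefficient) between initial bone mass, physical activity, grip strength, and change in BMC". No interaction term is specified.

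The Protocol (Group Assignment) allocates 20 women to each group by drawing sealed envelopes and describes no stratification on baseline bone. The SAP applies the same analysis to both experiments, with strain rate replacing strain magnitude in the second.

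**The concern.** Two versions of the same primary contrast are foreseen, one with initial BMC and one without. The plan does not say which one governs, or when a potential covariate is kept. That leaves a choice in the primary result that could be made after the data are seen.

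The variable is an obvious one to fix in advance. It must be measured for a change score to exist at all, and the SAP itself expects it to be inversely associated with the change. Without it, the group contrast carries whatever baseline difference the allocation happened to produce, and some explainable variance stays in the error term.

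There is a further issue outside the randomised comparison. If the analysed groups are not the groups as randomised, or if the predictor is the strain a woman achieved, a link between baseline bone and the predictor could bias the estimate and not merely widen its interval.

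**Working it through.** **Inputs from the documents.** 20 per group (Protocol, Group Assignment); two contrasts against control (SAP, Hypothesis 1a). With three groups of 20 analysed per experiment, residual degrees of freedom are 60 − 3 = 57 before any covariate, if all women are analysed.

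**Inputs not in the documents, hence assumed.** The correlation ρ of baseline BMC with 12-month change; two-sided alpha 0.05; 80% power; no dropout; absolute change. The SAP does not say whether change is absolute or percent. It gives no power calculation, so there is no figure of its own to reproduce.

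**Step 1: chance imbalance.** The SD of the difference in baseline means is √(2/20) = 0.316 baseline SD.

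**Step 2: variance saved.** Adjustment multiplies the residual variance by 1 − ρ². If baseline and follow-up have equal variance and correlate at r, then ρ = −√((1 − r)/2) and the variance ratio is (1 + r)/2.
- r = 0.90: ρ = −0.224, ratio 0.95, saving 5%.
- r = 0.98: ρ = −0.10, ratio 0.99, saving 1%.

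**Step 3: what that buys.** Unadjusted, the difference detectable with 80% power is (1.960 + 0.842) × 0.316 = 0.886 SD of change. Power at that difference after adjustment is:
- 80.4% at r = 0.98 and 82.0% at r = 0.90;
- 83.6% at |ρ| = 0.3 and 89.9% at |ρ| = 0.5, if the Hypothesis 1b association is that strong.

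**Step 4: shift from a given imbalance.** The unadjusted contrast moves by |ρ| × imbalance. One standard error of imbalance (0.316) moves it by 0.10 × 0.316 = 0.032 SD of change at r = 0.98, and by 0.224 × 0.316 = 0.071 at r = 0.90. The contrast's own standard error is √(2/20) = 0.316 SD of change. At |ρ| = 0.5 the shift is 0.158, or 0.310 for an imbalance of 1.96 standard errors.

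**Step 5: validity check.** In 4,000 simulated three-group trials of 20 per group for each setting, the unadjusted model rejected a true null in 5.1%, 4.6% and 5.4% of trials at |ρ| = 0, 0.3 and 0.5. Power without and with the baseline term was 79.4% and 78.6% at ρ = 0, 78.7% and 81.5% at 0.3, and 79.2% and 88.2% at 0.5. If ρ is zero, the term costs next to nothing.

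**Step 6: achieved strain.** The Protocol (2b, Mechanical Loading) says that the force needed for a given strain depends on each woman's bone geometry and strength. Target forces are individualised, so achieved strain need not track baseline bone if every woman meets her target. Where targets are missed or limited, it may. A woman with stronger bone would then reach a lower strain and, if Hypothesis 1b is right, also respond less. Two negative links multiply to a positive bias, so the strain slope would be exaggerated. The documents give no data to size this.

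**The case against.** The strongest reply is that Hypothesis 1b already says initial BMC will be added to the Hypothesis 1a models, and that an unadjusted change score in a randomised trial is valid. Both statements are right. What remains is that the addition serves a different hypothesis, is worded as optional, and is not tied to the primary result.

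Four stronger readings are tempting, and the documents do not support them.

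- *A reader might infer that the unadjusted contrast is biased.* Under intact randomisation it is not. Its standard error already allows for chance imbalance, and the simulated type I error is near 5%.
- *A reader might infer that the SAP says baseline BMC determines the change.* Hypothesis 1b predicts an association with a diminished response at a given strain. That is partly effect modification, and it is weak evidence for a main effect, especially in controls, for whom the SAP expects little change.
- *A reader might infer gains of 9% or 16%.* These need ρ = −0.3 or −0.4. From r = 1 − 2ρ², that means baseline-to-follow-up correlations of 0.82 or 0.68 under equal variances, well below 0.90.
- *A reader might infer that age must be adjusted too,* because the Protocol (Rationale for this population) says women "attain peak BMC and BMD at the ultra-distal radius at age 23 and 19 respectively", and women of 21 and 22 are eligible. Those figures are for the ultra-distal radius, not the whole radius. The Protocol adds that the measures stay at peak until 40. It gives no growth rate for ages 21 to 22, and a linear age term fits growth followed by a plateau poorly. Randomised controls also remove shared growth on average.

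**Conclusion.** The point holds as a gap in specification with a modest precision cost. It is not a flaw that invalidates the group comparison. Neither Hypothesis 1a model contains baseline BMC, and the SAP does not settle whether the primary contrast is adjusted.

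For the group contrast the expected gain is about 1% to 5% of variance. This rests on equal variances, absolute change, and an assumed baseline-to-follow-up correlation of 0.98 to 0.90. It is larger only if the Hypothesis 1b association proves strong.

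The case is stronger for the parts of the plan that randomisation does not protect: groups analysed without intention-to-treat, and the regression on achieved strain. There the risk is possible bias of unknown size. Baseline adjustment would reduce the part carried by baseline BMC, but it would not restore a randomised comparison.

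**What to change.** State in the SAP that both Hypothesis 1a models include, as a fixed covariate, the baseline value of the outcome being analysed: baseline whole radius total BMC for the primary outcome, and the matching baseline value for each secondary outcome. Name the adjusted contrast as primary and keep the unadjusted model as a sensitivity analysis.

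Under Hypothesis 1b, replace the optional main-effect wording for initial BMC with a prespecified baseline-by-group or baseline-by-strain interaction, since that is what a smaller response at a given strain implies. Do not add age on the strength of the Protocol's peak-bone figures.

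The main-model change costs one SAP line and one of about 57 residual degrees of freedom in the group regression. It needs no new measurement, because baseline BMC is already required to form the change score.
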